#### Certificate of Confidentiality N/A

## Provisions to Protect the Privacy Interests of Subjects

Should any participants desire not to interact with or provide personal information to specific members of the research team, they may report such a need to the PI and the arrangement of the research personnel will be adjusted accordingly. Participants will not be required to provide a reason if they desire not to do so. If changing of research personnel is not possible, the PI will discuss with the subjects about alternative solutions.

Each participant will be assigned a unique identification code. A master code identifier which links the identification code and personal information will be maintained separately from the study data. Subject information and de-identified study data are only accessible to named investigators in this protocol and authorized research personnel. All data and materials collected during this study are for research purposes only, and the data will be kept in strict confidence. No information will be given to anyone without permission from the subjects.

HRP-503a - TEMPLATE - Interventional Research Protocol 1.1.21 Protocol Title: Gut microbiota and hyperphagia in PWS Protocol Version Date: October 7, 2022

## F. Potential Direct Benefits to Subjects

There are no known direct benefits to subjects.

#### 5.0 Special Considerations

#### 5.1 Health Insurance Portability and Accountability Act (HIPAA)

We will ask participants for their consent so that designated members of the research team can review his/her medical record to retrieve medical history, medications, clinical and laboratory data related to PWS or hyperphagia. All received health information will be stored in an encrypted password-protected file which is stored on the university's secure server and will only be accessible to authorized research personnel.

#### 5.2 Family Educational Rights and Privacy Act (FERPA) N/A

## 5.3 Code of Federal Regulations Title 45 Part 46 (Vulnerable Populations)

A. Special Populations

N/A

5.4 General Data Protection Regulation (GDPR)

N/A

## 5.5 NJ Access to Medical Research Act (Surrogate Consent)

N/A

## 6.0 Data Management Plan

## 6.1 Data Analysis

Microbiome sequencing data will be analyzed based on the amplicon sequence variants (ASVs) [28] to determine the gut microbiota composition using QIIME 2 [29]. Shannon index and ASV richness will be used to assess alpha diversity. Principal coordinate analysis will be used to compare and visualize dissimilarity in gut microbiota structure between samples based on beta diversity (Weighted and Unweighted UniFrac distance) and statistical differences will be tested using permutational multivariate analysis of variance (PERMANOVA). PICRUSt 2 will be used to predict the functions of individual ASVs and the collective functions of the gut microbiota at the gene content and pathway levels [30]. Global functional profiles of the gut microbiota will be compared and visualized by principal component analysis. Repeat measures correlation will be used to assess the relationships between ASVs [31], followed by ASV clustering based on co-abundance patterns. Multivariate methods such as MaAsLin2, that allow adjustment for confounding variables and model the covariates as random effects, will be applied to interpret the relationship between ASVs / ASV co-abundance groups / functions and the clinical metadata.

Difference in continuous variables of metadata, such as measurements of hormones, blood inflammatory markers and total caloric intake, between week 0 and week 4 will be tested by Paired t-test (two-tailed) if meeting normal distribution or Paired Wilcoxon Signed-Rank test (two-tailed) if not meeting normal distribution. Difference in the continuous variables of metadata between male and female will be tested by Student's t-test (two-tailed) if meeting normal distribution or Mann-Whitney test if not meeting normal distribution. Fisher's exact test will be used to compare proportions of categorical metadata, such as data in the appetite and physical activity questionnaires, between male and female, and between Week 0 and Week 4. The false discovery rate will be applied for multiple testing, where appropriate.

HRP-503a - TEMPLATE - Interventional Research Protocol 1.1.21 Protocol Title: Gut microbiota and hyperphagia in PWS Protocol Version Date: October 7, 2022

Functional MRI data will be preprocessed with fMRI/PREP and analyzed with Statistical Parametric Mapping. Functional connectivity in the resting state will be extracted in the feeding related networks using the Conn Toolbox with a specific focus on connectivity between anatomically defined ROIs in the hypothalamus, insula, anterior cingulate, ventromedial/orbitofrontal prefrontal cortex, ventral striatum and amygdala. Activation to food (vs non-food) images will be assessed for responsivity in appetitive feeding networks by first modelling food stimulus presentations vs. non food presentations on a voxel wise basis and then extracting activations in anatomically defined regions of interest. The extracted data will then be analyzed as dependent variables following procedures like those described above.

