## D. Endpoints

[figure not shown]
- 1. Primary Outcome
  - Gut microbiota composition at Weeks 0 and 4
- 2. Secondary outcomes:

- Weeks 0, 1, 2, 3, and 4
  - a. Weight measured in pounds
- Weeks 0 and 4
  - a. Hormones related to satiety and hunger include ghrelin, peptide YY (PYY), leptin, glp-1/GIP, insulin, glucose
  - b. Inflammatory markers include c-reactive protein (CRP), interleukin 6 (IL-6) and tumor necrosis factor-alpha (TNF-), adiponectin
  - c. Outcome of fMRI showing responsivity of appetite feeding networks in the brain
  - d. Caloric intake recorded in MyFitnessPal application
  - e. Appetite behavior measured by hyperphagia questionnaire and visual analog scale (VAS)
  - f. Physical activity measured by physical activity questionnaire

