HRP-503a - TEMPLATE - Interventional Research Protocol 1.1.21 Protocol Title: Gut microbiota and hyperphagia in PWS Protocol Version Date: October 7, 2022

intervention gut microbiota was without effect. This piece of causality evidence showed that at least some of the major metabolic phenotypes associated with PWS can be transferred to germ-free mice along with the transplanted gut microbiota (5, 15).

**Dietary fibers selectively** promoted acetate and butyrate producers and structured a healthier gut ecosystem. Patients with type 2 diabetes were randomized to receive either the high-fiber WTP diet (W group; N=27) or usual care (U group; N=16) for 84 days (16). We identified 141 bacterial genomes that had the genetic capacity for fermenting dietary fibers. Intriguingly, only 15 of them were able to take advantage of the fibers and increased their abundance, while 79 remained unchanged and 47 were suppressed during the high-fiber intervention. All 15 positive responders possessed the pathways to produce acetate, and some could also produce butyrate. When the gut microbiota was

dominated by these bacteria, there was a concomitant reduction in bacteria that produced metabolically detrimental compounds (e.g. LPS, hydrogen sulfide and indole) and collectively these microbial changes led to improved metabolic outcomes (Figure 3). Acetate and butyrate can stimulate the production of GLP-1 and PYY; LPS can induce systemic inflammation; indole and hydrogen sulfide can inhibit the production of GLP-1 and PYY (17, 18). Shifting of the abundance of producers of these bioactive compounds may drive the improvement of metabolic phenotypes. It would be interesting to assess if appetite regulation and feeding behavior are also modulated by these high fermentable fiber-induced changes in gut microbiota.

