## 1.5 Sample Size Justification

No power calculation is performed for this pilot study. We aim to recruit 10 patients with hyperphagia(5 male and 5 female) to capture a reasonable degree of variations in gut microbiota composition.

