## 1.8 Specimen Collection

## A. Primary Specimen Collection

## Types of Specimens:

- Stool. Each participant will be provided with kits to collect fecal samples at home in Week 0 and Week 4. The fecal sample collection kit has been cleared by FDA for at-home use. Instructions and supplies will be provided to collect these samples at home (Appendix D).
- 2) Blood. Venous blood draws (10 ml each) will be taken during the baseline and Week 4 post-intervention meal tests (T=0, 30, 60, 120, 180 and 240 min of each test) at IFNH by qualified professionals including phlebotomists, registered nurses and physicians.
- Annotation: Data to be annotated or associated with each specimen will include participant code, age, sex, ethnicity, medical history, and medications.

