## Hospitalization during study

If patients are hospitalized during the study, they will be removed from the study and discontinue all data and sample collection. Subjects will need to contact the study PI, [name], D.O. at [name] if hospitalized during the study.

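### The PERMANOVA for the primary outcome in section 6.1 has no within-participant permutation rule; run plainly, it is conservative for Week 0 v Week 4

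*Combined protocol and SAP*

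**What the plan says.** Section 1.3 D lists one primary outcome: "Gut microbiota composition at Weeks 0 and 4". Section 1.3 B collects stool at those two times, and section 1.5 plans 10 participants in a single arm, so up to 20 samples in 10 pairs.

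For overall composition, section 6.1 compares samples on weighted and unweighted UniFrac distance, and "statistical differences will be tested using permutational multivariate analysis of variance (PERMANOVA". It adds no participant term, strata or permutation scheme.

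Dependence is handled unevenly elsewhere in section 6.1:

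- Week 0 v Week 4 differences in continuous metadata "will be tested by Paired t-test (two-tailed) if meeting normal distribution or Paired Wilcoxon Signed-Rank test".
- Categorical metadata at the same two weeks are compared by Fisher's exact test, with no mention of pairing.
- "Repeat measures correlation will be used to assess the relationships between ASVs", which is a different question.
- MaAsLin2, with random effects, is for relating microbiota features to clinical metadata.

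None of these tests the overall shift between weeks.

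**The concern.** PERMANOVA gets its p-value by reshuffling labels. If all 20 week labels are shuffled freely, many reshuffles set different people against each other, and between-person variation enters the reference distribution. The observed week contrast contains none of that variation, because each person contributes one sample to each week. The observed statistic is then judged against too wide a yardstick.

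At stake is the only named test of whether the supplement period was accompanied by an overall change in the microbiota. With 10 people, power given away needlessly could turn a real shift into a report of no change. An open permutation scheme could also be settled after the data are seen.

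**Working it through.** **Inputs.** From the documents: 10 participants with two samples each, and PERMANOVA on two UniFrac distances. Not in the documents, so assumed: alpha 0.05, the within-person correlation (ICC, written ρ), and the size and pattern of the shift. Section 1.5 says "No power calculation is performed for this pilot study", so there is no planned figure to reproduce.

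**Step 1: direction.** Take squared Euclidean distance and one feature with variance 1, n = 10 pairs, N = 20 samples and no true shift.

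- Observed among-week sum of squares: (n/2) × (mean difference)². Each person's difference has variance 2(1 − ρ), so the expectation is (n/2) × 2(1 − ρ)/n = 1 − ρ.
- Free permutation: the mean over reshuffles is SS_total/(N − 1). The expected SS_total is N − (1 + ρ) = 19 − ρ, which gives (19 − ρ)/19.
- Swaps within person keep each difference and change only its sign, so the expectation is again 1 − ρ.

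| ρ | Observed, 1 − ρ | Free reference, (19 − ρ)/19 | Ratio |
|---|---|---|---|
| 0 | 1.000 | 1.000 | 1.00 |
| 0.3 | 0.700 | 0.984 | 0.71 |
| 0.5 | 0.500 | 0.974 | 0.51 |
| 0.7 | 0.300 | 0.963 | 0.31 |

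A ratio below 1 means the observed statistic sits low in the free reference distribution even when nothing has happened. Within-person swaps give a ratio of 1 at every ρ.

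**Step 2: size, Euclidean and Bray-Curtis.** 10 pairs, 40 features, 499 permutations, shift of 0.5 SD in 10 features. Entries are free v within-participant, in %.

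| ρ | Type I, Euclidean | Type I, Bray-Curtis | Power, Euclidean | Power, Bray-Curtis |
|---|---|---|---|---|
| 0.3 | 0 v 4.6 | 0.5 v 4.8 | 3.3 v 51.5 | 3.2 v 14.3 |
| 0.5 | 0 v 4.6 | 0.1 v 3.6 | 0.2 v 68.3 | 0 v 17.5 |
| 0.7 | 0 v 4.6 | 0 v 6.2 | 0 v 92.7 | 0 v 28.5 |

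At ρ = 0 the free test was nominal (5.3% and 4.8%). A further simulation with both distances at ICC 0.3 to 0.7 gave type I error of 0 to 0.4% free v 3.6 to 5.2% restricted, and power of 0 to 9% v 22 to 36%.

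**Step 3: size, UniFrac.** 141 taxa on random trees, 5,000 reads, 499 free permutations v all 1,024 swaps. The responder pattern borrows the counts in section 1.4, "only 15 of them were able to take advantage of the fibers and increased their abundance, while 79 remained unchanged and 47 were suppressed". They come from a type 2 diabetes study and are an assumption here. Power is free v within-participant, in %.

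| ICC | Weighted, 1.5 SD shift | Unweighted, 1.5 SD shift | Weighted, shift set for about 80% | Unweighted, shift set for about 80% |
|---|---|---|---|---|
| 0.3 | 29.8 v 36.6 | 78.3 v 84.6 | 80.0 v 81.4 | 75.3 v 80.6 |
| 0.5 | 18.2 v 33.2 | 52.8 v 71.4 | 76.7 v 80.5 | 70.7 v 84.5 |
| 0.7 | 8.4 v 29.0 | 16.2 v 48.2 | 72.0 v 80.4 | 54.0 v 82.1 |

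The SD is the within-person SD. Two repeats of the 1.5 SD and null settings with separately written code agreed broadly. Across all three runs, free type I error was 1.9 to 3.2% at ICC 0.3, 0.7 to 1.3% at 0.5 and 0.2 to 0.8% at 0.7. Where reported, restricted type I error was 4.2 to 6.2%.

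**Step 4: range of the loss.** At ICC 0.3 the smallest loss is 81.4 − 80.0 = 1.4 points (weighted UniFrac) and the largest is 51.5 − 3.3 = 48.2 points (Euclidean). At ICC 0.7 the corresponding figures are 80.4 − 72.0 = 8.4 and 92.7 − 0 = 92.7 points.

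**Step 5: feasibility.** With m complete pairs there are 2^m swaps. Exchanging all labels leaves the statistic unchanged, so the smallest p is 2/2^m: 2/1024 = 0.002 at m = 10, 2/64 = 0.031 at m = 6 and 2/32 = 0.0625 at m = 5. Pairs can be lost: for anyone hospitalised, section 4.7 E says "they will be removed from the study and discontinue all data and sample collection".

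**The case against.** The strongest reply is that the plan is silent rather than wrong. Nothing in section 6.1 rules out blocking. Section 1.8 A keeps the link that it needs ("Data to be annotated or associated with each specimen will include participant code"), so an analyst could still block. With two sampling times and one arm, the week contrast is also easily inferred. Both points stand. The gap is the permutation scheme, and the harm arises only if the plain test is run.

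Four stronger readings are tempting, and the documents do not support them.

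- **That pairing was deliberately left out**, since paired tests are named for continuous data. The unpaired Fisher's exact test for the same two weeks undercuts this. The wording on dependence is uneven, so neither intention nor correct handling can be inferred.
- **That false positives are inflated.** For the week contrast the error runs the other way. A male v female PERMANOVA on all 20 samples would be anti-conservative (17.5 to 67.7% in the step 2 simulation at ρ 0.3 to 0.7), but section 6.1 does not state that PERMANOVA contrast.
- **That the loss is small at ICC 0.3 and large only at 0.5 to 0.7.** This holds only in the UniFrac model of step 3; the Euclidean result at 0.3 contradicts it as a general rule.
- **That blocking would make the study well powered.** Weighted UniFrac at the 1.5 SD shift reaches only 29 to 37% with blocking.

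It is also fair to say that a clarification in a 10-person pilot is a modest matter. Against that, this is the only named test of the primary outcome's overall shift.

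**Conclusion.** The point holds as an under-specified primary analysis with a known direction of error. If a person's two samples are positively correlated, plain PERMANOVA rejects less than 5% of the time under the null for Week 0 v Week 4, and it loses power. With no such correlation the plain test is nominal and nothing is lost.

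The direction rests only on positive within-person correlation. The size rests on ICC, shift, distance, tree, read depth and alpha, none of which the documents give. The simulated loss of about 1 to 50 points at ICC 0.3, often larger at 0.5 to 0.7, is therefore illustrative.

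The consequence is limited. Section 1.1 A frames the work as exploratory, there is no power calculation, and no decision rule depends on this p-value. It should still be fixed, because the better method is concrete and nearly free.

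**What to change.** Add to section 6.1:

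- The Week 0 v Week 4 difference in weighted and unweighted UniFrac distance will be tested by PERMANOVA on participants with both samples, with permutations restricted within participant (all 2^m swaps for m complete pairs).
- The report will give m and the smallest attainable p, 2/2^m.
- State whether FDR is applied across the two distances. If it is, a lone signal at m = 6 can adjust to 2 × 0.031 = 0.0625, so 5% may be out of reach there as well as at m = 5 or fewer.
- Where 5% cannot be reached, the shift is reported descriptively.
- Any shift is worded as a change over time, because blocking does not replace a control arm.

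Cost: a few sentences and a small change in code, with no new data or visits. Participants without both samples drop out of this test. If there is no within-person correlation, restriction costs a little power: 0 to 2.4 points in the UniFrac runs and up to 7 points in a Euclidean check.

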## A. Objectives

To use high-fiber supplementation, an intervention known to create shifts in the gut microbiota towards a healthier structure, to explore the relationship between gut microbiota, appetite control and feeding behavior in patients with hyperphagia syndrome.

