TESTING AND INTERVENTION. Participants will attend a baseline visit at the Center for Advanced Human Brain Imaging Research (CAHBIR) at Rutgers University, during which functional magnetic resonance imaging (fMRI) coupled with a meal test will be performed to assess peripheral and central feeding pathways (7, 8). fMRI scans will be performed during resting state to assess functional connectivity of feeding related networks, with a specific focus on connectivity between the hypothalamus, insula, anterior cingulate, ventromedial/orbitofrontal prefrontal cortex and amygdala (9, 10). Activation to food (vs non-food) images will be assessed to index responsivity to appetitive feeding networks including the above regions and the ventral striatum using paradigms that have previously been found to be sensitive to trait and state in multiple studies (11-13). Thereafter participants will consume a liquid meal (525 kcal; Ensure Plus, Abbott). fMRI will be repeated immediately after the meal. Participants will attend a second visit at the IFNH, during which laboratory work coupled with a meal test will be performed to assess satiety hormones and inflammatory markers. Fasting blood draw will be taken, and the participants will consume a liquid meal (525 kcal; Ensure Plus, Abbot) followed by blood draws at 30, 60, 120, 180 and 240 min postmeal. Upon completion of baseline testing and providing a fecal sample, participants will consume NBT-NM108 (a mixture of inulin, Fibersol-2, and brans of oat, wheat, corn and sorghum; Notitia Biotechnologies) daily for 4 weeks. At the completion of the 4-week intervention, all sampling and testing will be repeated as per baseline. At baseline and end of intervention, participants will be interviewed with appetite and physical activity questionnaires (Appendix C and G) and requested to complete a 24-h food recall using MyFitnessPal, a mobile health app on their phone.

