## B. Data Points

- Gut microbiota composition: fecal samples will be collected at weeks 0 and 4.
- fMRI scans will be completed at baseline and end of intervention.
- Blood parameters (satiety hormones and inflammatory markers) at minutes 0, 30, 60, 120, 180, and 240 post-meal at week 0 and week 4.
- Appetite and physical activity questionnaires at weeks 0 and 4.
- Calorie count calculated via 24-h food recall on MyFitnessPal at weeks 0 and 4.

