## **1.4 Preliminary Data**

Dietary fibers modulated gut microbiota and conferred clinical benefits in PWS patients. Children aged 3-16 years old (N=17 with PWS and N=12 with simple obesity) were prescribed a diet enriched with wholegrains, traditional Chinese medicinal foods and prebiotics (WTP diet) for 30-90 days (5). This diet was specifically formulated to include a large amount of dietary fibers with diverse physicochemical structures to maximize carbohydrate fermentation by the gut microbiota. The diet induced significant and yet

similar shifts in the overall gut microbiota structure in both groups, an effect associated with improvements in metabolic parameters including body weight and glucose homeostasis (Figure 1). Importantly, based on a hyperphagia questionnaire, we observed a modest but non-significant improvement in the overall food-related behavior in PWS patients (P=0.074).

Our network analysis identified guild-level structure in the gut microbiota (Figure 2). When supplemented with dietary fiber, gut bacteria exhibited co-abundance patterns and formed genome interaction groups (GIGs) or "guilds" (an ecological group in which members exploit an environmental resource in a similar way and show co-abundant behavior). Three guilds, which included strains of beneficial bacteria such as Bifidobacterium were negatively correlated with body weight and HbA1c, while 9 guilds which contained many opportunistic pathogens such as LPS producers were positively associated with disease parameters. Taken together, we showed that high-fiber diet was a feasible and effective way to modulate gut microbiota in PWS patients, which conferred clinical improvements and may also alleviate hyperphagia.

[figure not shown]

Figure 2. Network analysis of the bacterial genomes. Genomes of the same color were grouped in the same guild. Size of the nodes indicated the abundance of genomes. Red and blue lines denoted positive and negative correlations respectively.

[figure not shown]
Interestingly, transplantation of the pre- and post-intervention gut microbiota from the same patient to germfree mice induced opposite responses in the recipient mice. While these mice had no genetic defects and were maintained on a standard chow diet, receiving the pre-intervention PWS gut microbiota alone was sufficient to induce inflammation, excessive fat accumulation and liver steatosis whereas the post-

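### With stool sampled only twice per person and no Week term, the planned repeated measures correlation between ASVs can largely reflect the common shift on fibre rather than co-abundance

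*Combined protocol and SAP*

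**What the plan says.** Section 6.1 (Data Analysis) gives the network step in one sentence: "Repeat measures correlation will be used to assess the relationships between ASVs [31], followed by ASV clustering based on co-abundance patterns". The resulting groups then enter MaAsLin2, alongside single ASVs and predicted functions, to be related to the clinical data.

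The sampling schedule is in section 1.3 B (Data Points): "Gut microbiota composition: fecal samples will be collected at weeks 0 and 4". Section 1.8 agrees: "Each participant will be provided with kits to collect fecal samples at home in Week 0 and Week 4". On sample size, section 1.5 says "We aim to recruit 10 patients with hyperphagia(5 male and 5 female") and "No power calculation is performed for this pilot study".

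There is one arm. Section 1.3 A says that after baseline testing "participants will consume NBT-NM108" daily for four weeks, and section 1.1 A calls fibre supplementation "an intervention known to create shifts in the gut microbiota towards a healthier structure". Section 1.4 defines a guild as "an ecological group in which members exploit an environmental resource in a similar way and show co-abundant behavior".

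For the correlation step, section 6.1 names no Week term and no centring of changes. The test it names for microbiota structure is PERMANOVA on whole-community distances. The paired t-test or Wilcoxon test is for the metadata, such as hormones and calories. No test of each ASV's own shift is named. The method is cited to item 31, but the bibliography ends at 18, so the documents do not show whether a different variant is intended.

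**The concern.** Repeated measures correlation removes each person's average level and then fits one common slope. With many samples per person, that captures how two ASVs move together over time. With two samples, each person contributes one change per ASV, and the average change over all participants stays in the statistic. The participant term does not remove it.

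Everyone takes fibre between the two samples, and a shift is the trial's premise. Two ASVs that both rise on average can therefore correlate strongly although a larger rise in one says nothing about the other. Two competitors that both rise on average, but trade off from person to person, could be placed in the same group.

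At stake is the guild structure that the trial would report, and the group-level part of the MaAsLin2 analysis. Groups that mostly encode week will tend to track any clinical measure that also changed over the four weeks, unless Week is modelled there.

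**Working it through.** The plan gives no figure for this analysis, so there is nothing to reproduce.

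**Inputs.** From the documents: k = 2 samples per person (sections 1.3 B and 1.8), N = 10 (section 1.5), one arm (section 1.3 A). Assumed, because the documents are silent: a two-sided 5% level per pair, normally distributed changes, and a standardised shift δ (mean change divided by the between-person SD of change) from 0 to 3.

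**Step 1: what the statistic is.** With two samples, each person's deviations from their own mean are ±d/2, where d is the change. The within-person sums of products are then half the sums over changes, and the halves cancel:

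r = Σ(dx·dy) / √(Σdx² · Σdy²), with df = N(k − 1) − 1 = 10 × 1 − 1 = 9.

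The mean changes are not subtracted. In three simulated data sets (independent changes, δ = 1), the fitted repeated measures r was 0.399, 0.431 and 0.616, equal each time to this formula. Adding Week gave 0.023, −0.286 and −0.122, equal each time to the ordinary centred correlation of the changes, with 8 df.

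**Step 2: large-sample value.** If ρ is the true correlation of changes and the two ASVs shift by δA and δB,

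r → (ρ + δA·δB) / √((1 + δA²)(1 + δB²)).

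For ρ = 0 and equal shifts this is δ²/(1 + δ²); for δ = 1 it is 1/2 = 0.50.

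**Step 3: simulation at N = 10** (200,000 replicates per row, ρ = 0, same shift in both ASVs). The critical |r| is t/√(df + t²): 0.602 at 9 df and 0.632 at 8 df.

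| δ | δ²/(1 + δ²) | Mean r, as planned | Flagged, as planned | Flagged, Week added |
|---|---|---|---|---|
| 0 | 0.00 | 0.00 | 5.0% | 5.0% |
| 0.25 | 0.06 | 0.06 | 5.2% | 4.9% |
| 0.5 | 0.20 | 0.20 | 8.5% | 5.0% |
| 0.75 | 0.36 | 0.36 | 18.8% | 5.0% |
| 1.0 | 0.50 | 0.51 | 36.9% | 5.0% |
| 1.5 | 0.69 | 0.70 | 79.3% | 5.0% |
| 2.0 | 0.80 | 0.81 | 97.6% | 5.1% |
| 3.0 | 0.90 | 0.91 | 100% | 5.0% |

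Other settings:
- Only one ASV shifts (by 1 or 2 SD): 5% flagged.
- Opposite shifts (+1 and −1): mean r −0.51, 37% flagged, all negative.
- ρ = −0.7 with both shifting by 2 SD: the limit is (−0.7 + 4)/5 = 0.66 and the simulated mean r is +0.69, so the sign reverses.
- ρ = 0.7 with no shift: mean r 0.68, 73% flagged, so real co-variation still registers.

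**Step 4: clustering.** 60 ASVs in four true groups of 15; within each group five shift up by δ, five do not shift and five shift down; average linkage on 1 − r; 200 replicates. Agreement is the adjusted Rand index (1 is perfect, 0 is chance), using four clusters against true group and three against shift direction.

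| Within-group ρ | δ | Planned v true group | Planned v shift direction | Week added v true group |
|---|---|---|---|---|
| 0.5 | 0 | 0.60 | −0.02 | 0.55 |
| 0.5 | 0.5 | 0.41 | 0.08 | 0.53 |
| 0.5 | 1.0 | 0.08 | 0.44 | 0.54 |
| 0.5 | 1.5 | 0.02 | 0.51 | 0.53 |
| 0.8 | 0 | 0.96 | −0.03 | 0.93 |
| 0.8 | 0.5 | 0.84 | −0.01 | 0.94 |
| 0.8 | 1.0 | 0.25 | 0.39 | 0.92 |
| 0.8 | 1.5 | 0.06 | 0.52 | 0.91 |

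The simulations ignore compositional effects and excess zeros.

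**The case against.** **A shared response to fibre may be what a guild is.** Section 1.4 describes guilds as forming under fibre supplementation, with members that use a resource alike. Total within-person association is then a legitimate target, and centring deletes part of it. This stands as a reason to report both versions rather than replace one. It does not rescue the unadjusted clusters as evidence of co-abundance: the definition also asks for co-abundant behaviour, and the sign reversal above shows that a common rise can hide a trade-off.

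**The 37% and 79% are not error rates of the planned procedure.** That is correct. Section 6.1 clusters; it sets no 5% test per pair and applies the false discovery rate only where judged appropriate. The rates measure how far the statistic is biased. False discovery control would not cure this, because it needs valid p-values to start from.

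**Most pairs may be unaffected.** In the type 2 diabetes trial in section 1.4, 15 of 141 fibre-capable genomes rose, 47 fell and 79 did not change. At those fractions both members shift in (62 × 61)/(141 × 140) = 19% of pairs, and in the same direction in (15 × 14 + 47 × 46)/(141 × 140) = 12%. This is a fair limit on reach, though it comes from another disease and an 84-day diet. The affected pairs are those among responders.

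**It is an exploratory step in a 10-person pilot.** The primary outcome is composition. A reader might infer that all later functional and clinical analysis passes through the clusters; it does not. PICRUSt 2 is applied to individual ASVs and the whole community, and MaAsLin2 takes ASVs and functions as inputs in their own right. A reader might also infer that the mean shift of each ASV is already tested elsewhere; no such test is named.

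**Conclusion.** The concern holds as a conditional risk. The identity in step 1 is exact for two samples per person and no Week term. Its effect depends on shift size, which the documents do not give: negligible at 0.25 SD, small at 0.5 SD, substantial at 1 SD and near certain from 2 SD. In the clustering simulation, shift direction outweighs true group membership from about 1 SD.

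Two stronger readings are tempting and not supported. One is that any two ASVs that shift will look co-abundant: the shifts must be in the same direction and large relative to the between-person SD of change, since opposite shifts give negative correlation and a shift in only one ASV does nothing. The other is that the clusters would only restate the mean shift: person-to-person covariance also enters r and dominates when shifts are small (index 0.84 with the true groups at 0.5 SD and ρ = 0.8).

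The change should be made before analysis, because the trial expects a shift and the unadjusted clusters cannot show which of the two they reflect.

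**What to change.** In section 6.1:

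1. Add Week to the repeated measures model (equivalently, correlate mean-centred changes), state the 8 df, and cluster on those correlations.
2. Report these clusters beside the unadjusted ones. Describe as co-abundance guilds only groups that persist after Week adjustment, and describe the others as groups with a shared mean response to fibre.
3. Report each ASV's mean week 0 to week 4 shift separately.
4. Supply the missing reference for the method.

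The cost is wording, a few lines of code and one degree of freedom. With no mean shift, power per pair goes from 36% to 33% at a true correlation of 0.5 and from 73% to 68% at 0.7, before any false discovery control. With 10 people that is limited, and the plan should say so. Fewer and less tidy clusters are likely.

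As a secondary suggestion, name a centred log-ratio transform with a rule for zeros, since sequencing abundances are relative. For example, an assumed bloom of one ASV from 5% to 25% lowers every other ASV's share by 1 − 0.75/0.95 = 21% with no real change in them. The effect of this on the clustering was not computed.
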